8.3.3 Drug Accountability Procedures

Atorvastatin injection, labeled for investigational use, will be provided by Cumberland Pharmaceuticals Inc. The investigator is required to keep complete and accurate records of the receipt, dispensation, disposal and return of all clinical trial drugs provided during the conduct of the study.

For subjects entering the study already taking oral atorvastatin, the product will continue to be obtained according to the subjects' standard methods through the lead-in and follow-up periods. Accountability is not formally documented in these cases; however, in determining each subject's eligibility, the Investigator assures to the best of his or her knowledge that the subject has been on a stable dose of oral atorvastatin.

Subjects that were not taking oral atorvastatin when entering the study are provided it by the study at the assigned dose. Drug accountability for these subjects is calculated during the five-week lead-in period so that compliance for that patient is understood and eligibility can be confirmed.

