8.4.3.2 Exclusion Criteria_Treatment Phase

1. Clinically-significant elevation of ALT, AST, or CK during the Lead-in Period, as determined by the Investigator.
2. Known compliance for oral atorvastatin <90% during the Lead-in Period.
3. Failure to complete the pharmacokinetic blood draws (See [Section 9.3.4.1](#)) during the Lead-in Period.

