* Point of care LDL-C is the first procedure done after the subject gives consent. If the value does not meet eligibility, the subject screen fails and receives no other assessments. Otherwise, the subject continues into the full screening phase.

† On LI End Visit, the Point of Care LDL-C is performed first and, if the subject does not qualify for treatment, they are a screen fail and no other assessments are done.

‡ The CMP, including liver enzymes and CK results must be reviewed by an Investigator before the subject is deemed eligible for treatment. The LDL result from this panel will not weigh in on the eligibility determination. Only the point of care result from LI End Visit determines eligibility.

§ PK sampling (oral PK) is performed at the Lead-in End visit. Samples are taken per [Section 9.3.4.1](#). The pre-dose sample serves as the Hour 24 level.

¶ On Day 1, vitals are measured twice: 1) between 30 and 0 minutes before the start of IMP, and 2) 15 (\pm 5) minutes after the start of IMP

|| PK sampling (Multi-dose PK) is performed on subjects that complete a Day 15 visit. Samples are taken per [Section 9.3.4.2](#). The pre-dose sample serves as the Hour 24 level.

△ PK sampling (SC PK) is performed On Day 22 for those subjects participating in the sub-study. A subcutaneous injection of IMP is administered on a day that oral atorvastatin is withheld, then samples are taken per [Section 9.3.4.3](#).

** If a subject withdraws (WD) from the treatment period before Day 15, the following assessments should be completed: Physical exam, CBC, CMP, lipid profile, vital signs. Withdrawn subjects do not have PK blood draws and are not eligible for the SC sub-study.

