9.3 Key Study Procedures

9.3.1 Clinical Laboratory Assessments

Blood sample collection for routine laboratory assessments will be performed within protocol-specified time periods and according to the site's standard practices for drawing and processing samples. The analytes listed here in Table 9-2 are measured by the site's local laboratory and evaluated by the investigator for safety monitoring with respect to reference ranges provided by that lab:

Table 9–2a. Clinical Lab Analytes to be Measured at Screening, Lead-in End Visit and Day 15

Complete blood count (CBC) with differential	
Hematocrit	Neutrophils, absolute count
Hemoglobin	Lymphocytes, absolute count
Total white blood cell count	Monocytes, absolute count
Platelet count	Eosinophils, absolute count
	Basophils, absolute count
Comprehensive Metabolic Panel (CMP)	
Sodium	Albumin
Potassium	Total protein
Chloride	Aspartate aminotransferase (AST)
Total carbon dioxide (serum bicarbonate)	Alanine aminotransferase (ALT)
Glucose	Alkaline phosphatase (ALP)
Blood urea nitrogen (BUN)	Total bilirubin
Serum creatinine (SCr)	Creatine Kinase (CK)
Calcium	Lactate Dehydrogenase (LDH)
Lipid Profile	
Low-density lipoprotein cholesterol (LDL-C)	Total cholesterol
High-density lipoprotein cholesterol (HDL-C)	Triglycerides

b. Clinical Lab Analytes to be Measured at Day 3 and Day 8

Basic Metabolic Panel	
Blood urea nitrogen (BUN)	Aspartate aminotransferase (AST)
Serum creatinine (SCr)	Alanine aminotransferase (ALT)
Creatine Kinase (CK)	Alkaline phosphatase (ALP)
LDL-C (Day 8 only)	

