9.3.6.2.3 Subsequent Cohorts (20and 40 mg PO Atorvastatin)

Once two or more subjects from the 10 mg Lead-in group complete the study, the other cohorts can be opened to enrollment.

$LDL-C$ results from completed subjects in the 10 mg PO atorvastatin cohort provide information on the dose-response efficacy for the injectable route for atorvastatin that is helpful toward dosing the other Lead-in groups.

The targeted initial dose for each of the subsequent Lead-in cohorts is listed in [Table 9-4](#). However, any adjustments that were ultimately required for the dosing of the 10 mg PO cohort suggest that a similar adjustment is needed from the targeted doses for the other cohorts. Therefore, the starting dose for each subsequent cohort is adjusted accordingly by the sponsor prior to dosing the first enrolled subject of that treatment cohort.

With the activation of Protocol Amendment 3, dated 04Sep2019, one additional cohort is to be enrolled: Ten subjects that qualify for treatment following a lead-in period taking 20 mg oral atorvastatin are assigned to a daily dose of subcutaneous atorvastatin for the 15-day treatment phase.

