- Twenty-eight (+/- two) days following the first dose of oral atorvastatin (defined as Lead-in Day 0), the subject returns to the clinic for a Lead-in Interim Visit that includes a point-of-care LDL-C measurement and a review of drug compliance. Any compliance other than 100% prompts re-training of the subject. The subject is reminded to refrain from taking their oral atorvastatin at home on the day of the Lead-in End Visit.
- The Lead-in End Visit occurs 7 to 10 days after the Lead-in Interim Visit.
- A point-of-care LDL-C value is obtained and compared to the value from the Lead-in Interim Visit as per Inclusion Criterion 1b in [Section 8.4.3.1](#). If the comparison between values meets eligibility, the Lead-In End Visit continues including the oral pharmacokinetic assessments per [Section 9.3.4.1](#).

- In the event that the point-of-care analyzer gives an error message rather than a numerical result at the Lead-in Interim Visit, a blood sample may be submitted to the site's local laboratory and be available for comparison to a LDL-C value measured by the local lab at the Lead-in End Visit. Values taken by one method may not be compared to values taken by the other method.
- Other assessments are completed as per [Table 9-1B](#).

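### Under protocol Table 9-1B, a subject put on study-supplied oral atorvastatin who fails the Lead-in End LDL-C check leaves after 33 to 40 days with no scheduled CK, ALT or AST on that drug

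*Protocol*

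**What the plan says.** Protocol Table 9-1B covers two groups: subjects on no statin, and subjects on a statin other than atorvastatin. Section 8.3.3 states: "Subjects that were not taking oral atorvastatin when entering the study are provided it by the study at the assigned dose".

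Their laboratory schedule in lead-in is short.

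- **Screening** (up to 3 days before Lead-in Day 0): full panel and pregnancy test, before the first study-supplied dose.
- **Interim** (Day 28 ± 2): Section 9.4.2(b) describes a "Lead-in Interim Visit that includes a point-of-care LDL-C measurement and a review of drug compliance". No enzymes are listed.
- **Lead-in End** (7 to 10 days later): the full panel, including CK, ALT and AST, and the pregnancy test. Table 9-2a is headed "Clinical Lab Analytes to be Measured at Screening, Lead-in End Visit and Day 15", and Section 9.3.1 says that the analytes are "evaluated by the investigator for safety monitoring".

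Section 8.4.3.2 bars from treatment anyone with "Clinically-significant elevation of ALT, AST, or CK during the Lead-in Period", as judged by the Investigator.

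At the Lead-in End Visit the point-of-care LDL-C is done first. Inclusion criterion 1b (Section 8.4.3.1) requires it to lie between 75% and 125% of the Interim value. For a subject who fails, footnote † says "if the subject does not qualify for treatment, they are a screen fail and no other assessments are done". The body text agrees: "If the comparison between values meets eligibility, the Lead-In End Visit continues including the oral pharmacokinetic assessments". SAP Table 3B carries the same footnote.

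**The concern.** The study starts a drug, schedules one safety panel on it, and then cancels that panel because of a finger-stick LDL-C result. That result says nothing about muscle or liver. Section 5.5 of the protocol names rhabdomyolysis as a serious class risk that calls for monitoring while a statin is taken, and Section 11.1.1 counts an abnormal laboratory finding as a possible adverse event. If the test is not run, a symptomless rise in CK or transaminases cannot be found.

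The protocol treats a comparable subject differently. Someone withdrawn during the 15-day treatment period has the Table 9-2a panel drawn and, if of child-bearing potential, a urine pregnancy test (Section 9.4.4.7). A subject who fails at the end of lead-in, after a longer time on study-supplied atorvastatin, gets neither, and no reason is given.

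What is at stake is participant safety on a small scale. Nothing in the efficacy, PK or safety analyses depends on it.

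**Working it through.** The plan states no figure on this point, so there is none to reproduce. The check traces the schedule and then gauges how often the LDL-C check would fail by chance.

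**Time on drug at the check** (Section 9.4.2(b))

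- Shortest: (28 − 2) + 7 = 33 days
- Longest: (28 + 2) + 10 = 40 days
- Scheduled CK/ALT/AST in that time: none. Scheduled pregnancy tests: none.

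**Does another provision restore the panel?**

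- Table 9-1B footnote **: applies only to withdrawal from the treatment period.
- Section 10.2: worded broadly, but it refers back to the withdrawal visit already described, which Section 9.4.4.7 ties to the 15-day treatment period. Footnote † is the specific rule for these screen failures and says the opposite.
- Section 11.2: adverse events are asked about at each contact. This finds symptoms, not a silent enzyme rise.
- Section 9.4.7: a lead-in failure may be rescreened, with a new screening panel, but this is optional and needs sponsor approval.

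**Chance that a truly stable subject fails ±25%**

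Input: 9% LDL-C biological variability (Protocol 12.3), taken as the CV of each reading, with independent readings and no true change.

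- SD of the relative change = √2 × 0.09 = 0.127
- P(fail) = 2 × [1 − Φ(0.25 / 0.127)] = 4.95%
- Other forms: 5.1% (lognormal readings); 5.5% (simulated ratio of two normal readings)

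The documents give no device error, so the rows below the first are assumptions.

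| Assumption | Added device CV per reading | P(fail) |
|---|---|---|
| 9% per reading, no device error | 0 | 4.95% |
| SD of change 0.15 (the Day 15 planning SD in 12.1, borrowed) | √(0.15²/2 − 0.09²) = 5.6% | 2 × [1 − Φ(0.25/0.15)] = 9.56% |
| 12% per reading | √(0.12² − 0.09²) = 7.9% | 14.4% (simulated) |
| 15% per reading | √(0.15² − 0.09²) = 12% | 24.0% (simulated) |

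**Expected number of subjects, if the last cohort is still to enrol**

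Under Amendment 3, "one additional cohort is to be enrolled: Ten subjects that qualify for treatment following a lead-in period taking 20 mg oral atorvastatin". Expected failures before n subjects qualify are n × p / (1 − p). The share entering through Table 9-1B is not stated.

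- All ten, p = 4.95%: 10 × 0.0495 / 0.9505 = 0.52; P(at least one) = 1 − 0.9505¹⁰ = 39.8%
- All ten, p = 9.56%: 10 × 0.0956 / 0.9044 = 1.06; P(at least one) = 1 − 0.9044¹⁰ = 63.4%
- Five of ten, p = 4.95%: 5 × 0.0495 / 0.9505 = 0.26

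These are counts of people leaving without a panel, not of people harmed. The documents give no rate of enzyme elevation.

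**The case against.** The strongest reply is that the panel at this visit mainly decides who may be treated. Footnote ‡ requires CMP and CK review before a subject is judged eligible, and Section 8.4.3.2 is a treatment-phase exclusion. Once LDL-C has ruled the subject out, that purpose is spent. The lead-in drug is an approved oral product at 10 to 40 mg, and the documents set no enzyme schedule for oral dosing. This is fair, and it is why the point is an improvement and not a breach. It does not remove the safety-monitoring purpose stated in Section 9.3.1.

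The safeguards also stand. Myopathy history, hepatic impairment and AST or ALT above twice the upper limit are excluded before lead-in (8.4.2.2). Contraception is required (8.4.2.1), adverse events are asked about at each contact, and nothing forbids an unscheduled panel. What is left is chiefly a symptomless enzyme rise. Subjects switched from another statin stayed on it through screening (9.4.1), so they have enzymes on a statin, though not on the study-supplied one.

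The change may also come too late. SAP version 2.0 is dated March 2020, and the note under its Table 1 speaks of the fourth cohort's dosing in the past tense, although the text just above still uses the future. If that cohort is complete, the expected counts apply to nobody.

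A reader might infer more than the documents support:

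- **That Table 9-1A has the same problem.** Its footnote is identical, but those subjects stay on their own prescribed atorvastatin and were tested on it at Screening, 7 to 10 days earlier.
- **That the missed pregnancy test weighs as much as the enzymes.** These women tested negative at Screening, must use contraception and never receive the injection.
- **That about 3 to 5 subjects are affected.** That needs all 49 planned subjects (3 × 13 + 10) to enter through Table 9-1B: 49 × p / (1 − p) = 2.6 to 5.2. The documents do not say so.

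**Conclusion.** The gap is real and small. Table 9-1B footnote † and Section 9.4.2(b) cancel the only scheduled CK, ALT and AST on study-supplied oral atorvastatin for a subject who fails the LDL-C check after 33 to 40 days of it, and no other provision clearly restores them. It matters most for statin-naive subjects.

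About 5% of truly stable subjects would fail by chance. This assumes 9% variability per reading, independent readings and no device error; any device error raises it. The number of people affected cannot be fixed from the documents. It is about 0.5 to 1 if all ten subjects of the last cohort are still to enter through Table 9-1B, about 0.3 if half do (at 9% variability), and zero if that cohort is complete.

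A reader might take this as evidence of harm or as a threat to the results. Neither follows. No enzyme-elevation rate is given, and these subjects receive no injection, so they are in neither the safety nor the efficacy population. The point ranks as an optional, cheap improvement, held with medium confidence.

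**What to change.** Amend footnote † of protocol Table 9-1B and the matching sentence in Section 9.4.2(b). Failing the point-of-care LDL-C check should cancel only the oral PK draws and the treatment-phase procedures. The CMP with CK, ALT and AST already scheduled for that visit, and the pregnancy test for women of child-bearing potential, should still be done and reviewed by the Investigator. Clinically significant findings are recorded as adverse events under Section 11. The SAP Table 3B footnote is conformed only for consistency. No new listing is needed, and Table 9-1A can stay as it is.

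The cost is one footnote, its SAP copy and one sentence, with IRB approval as a protocol amendment (Section 15.2), plus one already scheduled panel for a subject who is already in the clinic. The downside is the laboratory cost and the follow-up of abnormal results in subjects who will not be treated. If enrolment is closed, carry the wording into the next protocol with this lead-in design.

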9.3 Key Study Procedures

9.3.1 Clinical Laboratory Assessments

Blood sample collection for routine laboratory assessments will be performed within protocol-specified time periods and according to the site's standard practices for drawing and processing samples. The analytes listed here in Table 9-2 are measured by the site's local laboratory and evaluated by the investigator for safety monitoring with respect to reference ranges provided by that lab:

Table 9–2a. Clinical Lab Analytes to be Measured at Screening, Lead-in End Visit and Day 15

Complete blood count (CBC) with differential	
Hematocrit	Neutrophils, absolute count
Hemoglobin	Lymphocytes, absolute count
Total white blood cell count	Monocytes, absolute count
Platelet count	Eosinophils, absolute count
	Basophils, absolute count
Comprehensive Metabolic Panel (CMP)	
Sodium	Albumin
Potassium	Total protein
Chloride	Aspartate aminotransferase (AST)
Total carbon dioxide (serum bicarbonate)	Alanine aminotransferase (ALT)
Glucose	Alkaline phosphatase (ALP)
Blood urea nitrogen (BUN)	Total bilirubin
Serum creatinine (SCr)	Creatine Kinase (CK)
Calcium	Lactate Dehydrogenase (LDH)
Lipid Profile	
Low-density lipoprotein cholesterol (LDL-C)	Total cholesterol
High-density lipoprotein cholesterol (HDL-C)	Triglycerides

b. Clinical Lab Analytes to be Measured at Day 3 and Day 8

Basic Metabolic Panel	
Blood urea nitrogen (BUN)	Aspartate aminotransferase (AST)
Serum creatinine (SCr)	Alanine aminotransferase (ALT)
Creatine Kinase (CK)	Alkaline phosphatase (ALP)
LDL-C (Day 8 only)	

9.3.2 LDL-C, Point of Care

A point-of-care analytical device (CardioChek® PA Analyzer, or equivalent) is used for the measurement of LDL-C levels when immediate results are required in order to make study-related

decisions. [Table 9-1A](#) and [Table 9-1B](#) designated the timepoints where a point-of-care LDL-C is measured. In each occurrence, a skin lancet is used to collect 1-2 drops of blood from the subject's finger. The instructional manual for the device will be followed for the assessment and LDL-C values will be documented, as required, in the source and/or the CRF.

9.3.3 Drug, Alcohol, and Viral Screening

During the screening visit, all subjects receive a urine drug screen and a saliva alcohol (ethanol) test. Subjects confirmed or suspected, in the Investigator's opinion, as abusing alcohol or non-prescription drugs are not eligible for the study.

Serology is performed to detect active infections of HIV, HBV, and HCV; positive subjects are not eligible to participate in the study treatment.

9.3.4 Pharmacokinetic Assessments

Allowable time windows for PK draws are shown below in [Table 9-3](#). Sampling taken outside of the allowable windows still contribute to building the pharmacokinetic profile, but minor deviations are captured in the Case Report Form (CRF).

Blood samples are taken by either direct venipuncture or via an indwelling catheter; however, samples must not be taken from the same catheter or any device used for administering the study drug.

Pharmacokinetic blood samples are collected for analyzing atorvastatin and metabolite concentrations in plasma.

If blood samples are obtained from an indwelling catheter rather than direct venipuncture, the catheter must be kept patent with saline flushes. A blood sample of approximately 1 mL will be drawn and discarded prior to each saved collection.

The samples are frozen in a -20°C freezer within 120 minutes of being drawn.

The actual sample collection date and time is entered in the eCRFs. Any issues with the sampling process will be noted.

Table 9–3 Allowable Time Windows for Pharmacokinetic Draws

Route being studied	Target time of blood draw	Allowable time window
Oral (screening period)	Pre-dose	-60 to -1 minutes before a dose of oral atorvastatin is taken

	Hour 0.5	\pm 5 minutes
	Hours 1, 2, 4, 6, and 8	\pm 10 minutes
Intravenous or Subcutaneous (Day 15)	Prior to the IV or SC dose	-60 to -1 minutes before the dose of IV or SC atorvastatin is taken
	Immediately after the IV or SC dose	3 to 7 minutes following the end of the administration
	Hour 0.5	\pm 5 minutes
	Hours 1, 2, 4, 6, and 8	\pm 10 minutes
Subcutaneous (Day 22)	Hour 0.5	\pm 5 minutes
	Hours 1, 2, 4, 6, 8	\pm 10 minutes
	Hour 24	\pm 60 minutes

9.3.4.1 Pharmacokinetics for Oral Dosing

Samples will be drawn from all participating subjects at the Lead-in End Visit in order to define the steady-state pharmacokinetic profile of the respective, stable dosing regimen on oral atorvastatin.

The subject is directed to refrain from taking their daily oral dose of atorvastatin at home, but then to bring the dose to the clinic for the PK visit. The visit is scheduled such that the dose is taken in the clinic at a time of day as close as possible to the time that the subject typically takes their oral dose.

At the oral PK visit, samples are drawn and processed per the procedure detailed above in [Section 9.3.4](#) at the following times; allowable windows are listed in [Table 9-3](#):

- Within 60 minutes prior to taking the oral dose of atorvastatin.
- At the following times after taking the oral dose:
 - 30 minutes
 - 1 hour
 - 2 hours
 - 4 hours
 - 6 hours
 - 8 hours

Levels of atorvastatin and metabolites measured from the pre-dose timepoint are imputed as the Hour 24 levels since the subject is on daily, constant dosing.

9.3.4.2 Pharmacokinetics for Multi-dose Intravenous or Subcutaneous Dosing (Treatment Phase)

Subjects receive their last dose of injectable atorvastatin at their Day 15 visit. Following the sampling and processing procedure detailed in [Section 9.3.4](#), samples are drawn at the following times relative to their last injectable dose; allowable windows are listed in [Table 9-3](#):

- Within 60 minutes prior to the start of the dose.
- At the following times after completing the dose:
 - Immediately after completion (**IV dose only**; subjects taking the SC dose under Amendment 03 omit this timepoint.)
 - 30 minutes
 - 1 hour
 - 2 hours
 - 4 hours
 - 6 hours
 - 8 hours

9.3.4.3 Pharmacokinetics for Subcutaneous Dosing (Sub-Study)

Subjects must first meet the eligibility criteria listed in [Section 8.4.4](#) before participating in the subcutaneous PK sub-study. The Investigator ensures the subject has given and documented their consent to participate in the sub-study before performing related procedures.

As a result of the review of real-time, open-label LDL-C values, the sponsor informs the Investigator as to which subject(s) qualify for the sub-study. This determination is made following the subject's Day 15 visit and the subsequent reporting of the LDL-C level from the visit. The Investigator inquires of the subject's ability and continued consent to participate in the sub-study (Inclusion Criteria).

Eligible subjects that have consented to the sub-study will have resumed taking daily oral atorvastatin at their lead-in dose since Day 16. They then return to the study center on Day 22 \pm 2 days after being instructed by the Investigator to refrain from taking their daily oral dose of atorvastatin at home on the day of the visit.

Subjects receive a subcutaneous dose of atorvastatin injection ([Section 8.3.2.2](#)), then samples are drawn at the following times after the time of the SC dose; allowable windows are listed in [Table 9-3](#):

- 30 minutes
- 1 hour

- 2 hours
- 4 hours
- 6 hours
- 8 hours
- 24 hours

